6.4 Efficacy

6.4.1 Efficacy assessment 1

The primary efficacy endpoint is defined as the time to the first confirmed occurrence of CV death, heart failure hospitalization* or outpatient heart failure**.

* *Heart failure hospitalization also includes the development of new symptomatic heart failure during an ongoing hospitalization including the index AMI hospitalization.*

** *Outpatient heart failure is defined as:*

- An urgent/unscheduled visit to an ED, acute/urgent care facility or outpatient clinic or a non-urgent office/practice or study visit for a primary diagnosis of HF that does not require an overnight hospital stay.
- Patients must exhibit at least one documented new HF symptom with objective evidence of clinical HF consisting of at least 2 physical examination findings or one physical examination findings and at least one laboratory criteria.
- The event requires initiation or intensification of treatment specifically for HF. Such treatment can include administration of intravenous agent (e.g., diuretic, vasodilator, vasopressor, or inotrope) or mechanical or circulatory intervention for HF, **OR** initiation of oral loop diuretic treatment, or intensification of oral maintenance loop diuretics for the diagnosis of HF, over a sustained period (i.e., initiation or doubling of

total daily dose through a period of ≥ 4 weeks), which is confirmed at a subsequent outpatient visit

6.4.2 Efficacy assessment 2

The secondary endpoints are:

- Time-to-first occurrence of CV death or HF hospitalization (days)
- Time-to-first occurrence of HF hospitalization or outpatient HF (days)
- Time-to-first occurrence of CV death, non-fatal spontaneous MI or nonfatal stroke (days)
- The cumulative number of composite events, including hospitalization due to HF, hospitalization due to non-fatal spontaneous MI, hospitalization due to non-fatal stroke and CV death. This endpoint is based on the total number of recurrent composite endpoints (count) and patient-specific follow-up time from randomization to end of study/death (days).
- Time to all-cause mortality (days)

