9.5.1 Efficacy variables

The secondary variables are defined as follows; the censoring mechanism will be the same as defined for the primary endpoint unless indicated otherwise:

- (1) Time from randomization to first occurrence of a confirmed composite of CV death or HF hospitalization
- (2) Time from randomization to first occurrence of a confirmed composite of HF hospitalization or outpatient HF (censoring will occur at the time of all-cause death)
- (3) Time from randomization to first occurrence of a confirmed composite of CV death, non-fatal spontaneous MI or non-fatal stroke
- (4) The cumulative number of composite events, including hospitalization due to HF, hospitalization due to non-fatal spontaneous MI, hospitalization due to non-fatal stroke and CV death. This endpoint is based on the total number of composite endpoints (count) and the patient-specific follow-up time from randomization to the last date the status of the patient was known (which could be the date of withdrawal from the study, the last visit prior to analysis cut off or the date of death).

(5) Time from randomization to all-cause mortality - patients without a death will be censored at the date of withdrawal from the study or the last day known to be alive (which may be established via telephone contact or the last visit prior to analysis cut off).

The secondary endpoints will be analyzed in order to compare LCZ696 vs ramipril using the ITT approach (i.e. estimation of the treatment effect under the ‘treatment policy’). Endpoints (1), (2), (3), and (5) will be analyzed using the same statistical analysis methods as specified for the primary analysis.

Secondary endpoint (4) will be analyzed using a negative binomial regression model with a Weibull baseline intensity function to allow flexibility if the baseline intensity is non-constant (Lawless, 1987). Treatment, STEMI/NSTEMI, PCI use at baseline and region will be included in the model as fixed effects. The relative rate ratio will be presented for LCZ696 vs ramipril together with 2-sided 95% confidence interval and 1-sided p-value.

Supportive analysis

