There are two points to be considered in the sample size re-estimation: the estimated lower event rates and a potentially higher hazard reduction in the primary endpoint. As shown in [Table 9-4](#) and [Table 9-5](#), the estimated event rates using blinded data are lower than the originally assumed event rates, for both the primary endpoint (see [Table 9-4](#)) and the double composite endpoint (see [Table 9-5](#)). An RRR of 19% is assumed for the primary endpoint in place of the original RRR of 18%. This change is based on the newly available efficacy data from the PIONEER-HF (CLCZ696BUS01) study in hospitalized patients with stabilized acute decompensated heart failure, which showed a 46% relative risk reduction (HR 0.54, 95% CI 0.37, 0.79) in patients treated with sacubitril/valsartan for 8 weeks compared to enalapril for an exploratory composite of serious clinical endpoint of death, rehospitalization for heart failure, implantation of a left ventricular assist device, and inclusion on the list of patients eligible for heart transplantation ([Velazquez, et al. 2019](#)). The observed risk reduction on the composite endpoint from the PIONEER-HF study was primarily driven by rehospitalization. Given a similar underlined pathophysiological mechanism between HFrEF and post-AMI with left ventricular dysfunction, and also acute setting for both PIONEER-HF and PARADISE-MI studies, this new data indicated that the effect size may have previously been underestimated.

Following the blinded sample size re-estimation, a sample size of 5,650 patients, randomized to LCZ696:ramipril using a 1:1 allocation ratio, has been chosen with the aim to obtain at least 708 first primary endpoint events and at least 592 first CV death or HF hospitalization events in this event-driven study. Seven hundred eight primary endpoint events will provide 80% power assuming a true Relative Risk Reduction (RRR) of 19% (i.e. a hazard ratio of 0.81) for LCZ696 vs ramipril with statistical testing at the overall 2.5% 1-sided type I error rate (with strong control of the FWER). Five hundred ninety two first CV death or HF hospitalization events will provide 77.5% nominal power assuming a true RRR of 20% (for the ITT analysis) for this double composite endpoint for the same type I error rate.

Additional assumptions are described below.

- 0.5% per year lost to follow-up rate (same as the original protocol assumption)

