- Recruitment duration of 37 months, and approximately 4 months follow-up for the last randomized patient are assumed (i.e., approximately 41 months for endpoint accrual).

Constant recruitment rates are assumed in each of the following time period based on the observed PARADISE-MI study data and projection: (1) 0 to 10 months, with a total of 463 patients randomized by month 10; (2) 10 to 24 months, with approximately a total of 2400 patients randomized by month 24; (3) 24 to 37 months, with 250 patients randomized each month.

- One interim analysis is planned to allow for stopping for efficacy, using a Haybittle-Peto boundary, thus 2.49% 1-sided alpha will be available for the final analysis, see [Section 9.7](#).
- Cumulative event rates for the primary composite endpoint at 3, 6, 12, and 18 months were derived based on Kaplan-Meier estimates using blinded data from all randomized patients in the PARADISE-MI study at the time of sample size re-estimation. Constant piecewise hazard rates were then derived accordingly for the following time periods: 0 to 3 months, 3 to 6 months, 6 to 12 months, and 12 to 41 months. The hazard rate for the time period of 12 to 41 months was derived through extrapolation of the 18 months cumulative event rate assuming a constant hazard rate during this time period. See [Table 9-4](#) for the cumulative event rates (pooled) based on the originally assumed event rates from [Table 9-1](#), as well as the estimated event rates from the blinded sample size re-estimation.

Table 9-4 Cumulative event rates (pooled) for the primary endpoint (first CV death, HF hospitalization or outpatient HF event)

Time from randomization	Cumulative event rate (original assumption) ²	Cumulative event rate (estimated using blinded data)
3 months	10.3%	7.2%
6 months	12.8%	8.6%
12 months	15.4%	11.0%
32 months ¹	20.1%	17.5%

¹ 32 months event rates were derived through extrapolation of the 18 months cumulative event rates, assuming constant monthly hazard rates from 12 to 32 months. The 18 months cumulative event rate was estimated to be 13.0% for the primary endpoint (first CV death, HF hospitalization or outpatient HF event).

² Cumulative event rates (pooled) were derived according to the original assumption of the control group rates in [Table 9-1](#).

Table 9-5 Cumulative event rates (pooled) for the double composite endpoint (first CV death or HF hospitalization event)

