Time from randomization	Cumulative event rate (original assumption) ²	Cumulative event rate (estimated using blinded data)
3 months	9.0%	6.0%
6 months	11.1%	7.5%
12 months	13.4%	9.6%
32 months ¹	17.6%	13.9%

¹ 32 months event rates were derived through extrapolation of the 18 months cumulative event rates, assuming constant monthly hazard rates from 12 to 32 months. The 18 months cumulative event rate was estimated to be 10.9% for the double composite endpoint (first CV death or HF hospitalization event).

Time from randomization	Cumulative event rate (original assumption) ²	Cumulative event rate (estimated using blinded data)
-------------------------	--	--

² Cumulative event rates (pooled) were derived according to the original assumption of the control group rates from [Table 9-1](#).

The sample size calculations were carried out using East version 6.4.

Power for secondary endpoints

[Table 9-6](#) summarizes the nominal power for secondary endpoints which will be included in the statistical testing strategy. A 1-sided alpha of 2.5% has been used for the calculations. All assumptions are based on the sample size re-estimation using blinded data.

Table 9-6 Summary of power to reject secondary endpoints' null hypotheses

Endpoint	Assumption about true treatment effect for LCZ696 vs ramipril for ITT analysis	Assumptions	Nominal power
(1) Time to first CV death or HF hospitalization	20% RRR	Expect 592 events ¹	77.5%
(2) Time to first HF hospitalization or outpatient HF	17% RRR	Expect 566 events ²	60.1%
(3) Time to first composite of CV death, non-fatal MI or non-fatal stroke	15% RRR	Expect 594 events ³	50.8%
(4) Total number of hospitalizations for HF, MI and stroke related reasons including CV death	17% reduction in rate ratio	Over-dispersion=6; Rate of events per year (pooled) = 0.192 ⁴	55.1%

¹ Event rates as per [Table 9-5](#), estimated using blinded data

² Cumulative event rates (pooled) for the composite endpoint (first HF hospitalization or outpatient HF event) at 3, 6, 12, and 18 months were estimated to be 5.4%, 6.6%, 8.3% and 10.3%, respectively. Constant piecewise hazard rates were derived accordingly for the following time periods: 0 to 3 months, 3 to 6 months, 6 to 12 months, and 12 to 41 months. The hazard rate for the time period of 12 to 41 months was derived through extrapolation of the 18 months cumulative event rate.

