³ Cumulative event rates (pooled) for the composite endpoint (first CV death, non-fatal MI or non-fatal stroke event) at 3, 6, 12, and 18 months were estimated to be 4.6%, 6.0%, 8.7% and 11.0%, respectively. Constant piecewise hazard rates were derived accordingly for the following time periods: 0 to 3 months, 3 to 6 months, 6 to 12 months, and 12 to 41 months. The hazard rate for the time period of 12 to 41 months was derived through extrapolation of the 18 months cumulative event rate.

⁴ For the power calculation the rate was assumed to be constant over time

The number of events were calculated for a sample size of 5,650 patients; 37 months recruitment and approximately 4 months minimum follow-up.

HF = Heart Failure; RRR = Relative Risk Reduction

The power calculations were carried out using East Version 6.4.

10 Ethical considerations

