³ Cumulative event rates (pooled) for the composite endpoint (first CV death, non-fatal MI or non-fatal stroke event) at 3, 6, 12, and 18 months were estimated to be 4.6%, 6.0%, 8.7% and 11.0%, respectively. Constant piecewise hazard rates were derived accordingly for the following time periods: 0 to 3 months, 3 to 6 months, 6 to 12 months, and 12 to 41 months. The hazard rate for the time period of 12 to 41 months was derived through extrapolation of the 18 months cumulative event rate.

⁴ For the power calculation the rate was assumed to be constant over time

The number of events were calculated for a sample size of 5,650 patients; 37 months recruitment and approximately 4 months minimum follow-up.

HF = Heart Failure; RRR = Relative Risk Reduction

The power calculations were carried out using East Version 6.4.

4 Change to protocol specified analyses

Not applicable

5 Appendix

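### Is the 55.1% power stated for the total-events secondary endpoint inconsistent with the 41-month design?

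*Protocol*

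**What the plan says.** Protocol Section 9.8.2 and SAP Section 3.2 set out the re-estimated design: 5,650 patients randomized 1:1, recruitment over 37 months in three phases, and "approximately 41 months for endpoint accrual". Table 9-6 (SAP Table 3-6) then lists nominal power for the four secondary endpoints in the testing hierarchy. "A 1-sided alpha of 2.5% has been used for the calculations".

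Rows (1) to (3) each print an expected number of events. Row (4), a count endpoint, prints none. It gives a 17% reduction, an assumptions cell that opens "Over-dispersion=6; Rate of events per year (pooled" (the rate is 0.192), and 55.1% power. Its only footnote adds: "For the power calculation the rate was assumed to be constant over time". The note under the table, "37 months recruitment and approximately 4 months minimum follow-up", describes how the numbers of events were obtained.

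Protocol Section 9.5.1 defines endpoint (4) by the event count and "the patient-specific follow-up time from randomization to the last date the status of the patient was known", which may be the date of death. Section 6.4.2 likewise runs follow-up to end of study or death.

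**The concern.** Power for a count endpoint needs a follow-up time, and row (4) states none. Solving for the one that returns 55.1% gives almost exactly 12 months. The endpoint is analysed over each patient's own follow-up, which averages about 17 months under the stated accrual, and that design gives a higher power. Row (4) would then rest on a different horizon from the three rows beside it, and a planning figure would misdescribe the design.

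The superseded table adds to the suspicion. Its 46% for the same endpoint fits that design's 20-month mean follow-up and not 12 months, so the convention may have changed without explanation.

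**Working it through.** **Inputs.** From Table 9-6: rate ratio 0.83, over-dispersion k = 6, pooled rate 0.192 per year, constant rate, one-sided alpha 0.025. From Section 9.8.2: 5,650 patients, so n = 2,825 per arm; 463 randomized by month 10, 2,400 by month 24, then 250 a month to month 37; loss to follow-up 0.5% per year. Mortality is not given, so every death rate below is an assumption.

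**Arm rates.** Ramipril 2 × 0.192/1.83 = 0.2098 per year; LCZ696 0.83 × 0.2098 = 0.1742. |ln 0.83| = 0.1863.

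**Reproducing 55.1%.** With a common follow-up of t years, Var(log rate ratio) = [1/(0.2098t) + 1/(0.1742t) + 2k]/n. At t = 1 this is (4.766 + 5.742 + 12)/2,825 = 0.007967, so SE = 0.08926. Power = Φ(0.1863/0.08926 − 1.960) = Φ(0.128) = 55.07%. Solving for 55.1% gives t = 12.0 months.

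**The 41-month design.** The information per patient is E[λF/(1 + kλF)], averaged over follow-up F. Under the stated accrual, mean F is 17.2 months.
- No attrition: 0.09998 (ramipril) and 0.09299 (LCZ696). Var = (10.00 + 10.75)/2,825 = 0.00735, SE = 0.0857, power = Φ(0.214) = 58.5%.
- With 0.5% per year loss: 58.4%.

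**Letting the unprinted inputs vary** (41-month design, 0.5% loss, k within the values that print as 6):

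| Assumption | k | Power |
|---|---|---|
| No deaths | 5.5 | 60.6% |
| No deaths | 6.49 | 56.3% |
| Deaths 3%/year | 6 | 57.7% |
| Deaths 6%/year | 6 | 57.1% |
| Deaths 10%/year | 6 | 56.3% |
| Deaths 6%/year | 6.49 | 55.1% |
| Deaths 3%/year plus 2.5% extra in the first 3 months | 6.4 | about 55.3% |

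The last line allows for early deaths because risk in this trial is front-loaded: the notes to Table 9-6 put first CV death, MI or stroke at 4.6% by 3 months and 8.7% by 12.

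**Another reading of the rate.** The superseded table used a ramipril rate (0.236). If 0.192 had been entered as the ramipril rate, despite its label, the 41-month design gives 56.9% with loss only and 55.9% with 4.5% per year mortality, both at k = 6.

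**Neighbouring rows.** Φ(√(d/4) × |ln HR| − 1.960) with 592 events at 0.80, 566 at 0.83 and 594 at 0.85 gives 77.5%, 60.1% and 50.8%, as printed.

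**Superseded row (4)** (k = 9, 0.236 per year, 2,325 per arm, printed 46%): 45.6% at a common 20 months, 44.7% with patient-specific follow-up, 40.4% at 12 months.

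**The case for a change.** The case for a correction is that every calculation confined to the printed inputs exceeds 55.1%. The 41-month design gives 58.4% with the stated loss, a cut at 43 months with no attrition gives 60.9%, and a common follow-up at the 19-month mean in Protocol Section 3.1 gives 63.1%. Rounding of the over-dispersion alone does not reach 55.1%, and at k = 6 neither does any constant death rate tried, up to 10% per year. The match at 12 months is close, and the superseded row followed its own design's follow-up. A footnote would be cheap.

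Most of this stands as arithmetic. A reader cannot reproduce row (4) from what is printed, and a one-year horizon is a reasonable guess. But a calculation without deaths is not the endpoint's calculation, because follow-up ends at death. Once deaths enter, the answer depends on a rate that the documents do not give, and combined with the rounding of k it can fall on 55.1%. Nor do the documents show how the software treated accrual, dropout or the variance. The 37-plus-4-month note is tied to event counts, which row (4) does not have, so no printed statement is contradicted. Restating the power as 56% to 58% would replace one undocumented assumption with another.

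**Conclusion.** No change is needed. The 55.1% lacks a stated follow-up and mortality assumption, which is a gap in documentation and not a demonstrated error. Against the 41-month design it is low by at most about 3.4 points (58.5% − 55.1%) at k = 6. The gap is roughly 1 to 3 points with constant mortality of 3% to 10% per year, and it closes under death rates and rounding that the documents do not exclude. Those death rates are assumed; the 12-month explanation is likewise an inference.

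Any discrepancy understates the power, so it is conservative. Endpoint (4) is tested last in the hierarchy and its power is labelled nominal. The sample size and event targets rest on the primary endpoint and the CV death or HF hospitalization composite, and the analysis uses actual follow-up whatever the planning calculation assumed. At 55% or 58% a planner draws the same conclusion: power for this endpoint is modest.

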10.1 Regulatory and ethical compliance

This clinical study was designed and shall be implemented, executed and reported in accordance with the International Council for Harmonisation (ICH) Harmonized Tripartite Guidelines for Good Clinical Practice, with applicable local regulations (including European Directive 2001/20/EC, US CFR 21, and Japanese Ministry of Health, Labor, and Welfare), and with the ethical principles laid down in the Declaration of Helsinki.

10.2 Informed consent procedures

Eligible patients may only be included in the study after providing written (witnessed, where required by law or regulation), Institutional Review Board/Independent Ethics Committee (IRB/IEC) approved informed consent, or, if incapable of doing so, after such consent has been provided by a legally acceptable representative(s) of the patient. In cases where the patient's representative gives consent, the patient must be informed about the study to the extent possible given his/her understanding. If the patient is capable of doing so, he/she must indicate assent by personally signing and dating the written informed consent document or a separate assent form. Informed consent must be obtained before conducting any study-specific procedures (e.g. all of the procedures described in the protocol). The process of obtaining informed consent must be documented in the patient eSource/source documents.*

[] For Germany only, the first paragraph will read as follows:*

Eligible patients may only be included in the study after providing written (witnessed, where required by law or regulation) IRB/IEC-approved informed consent. He/she should indicate assent by personally signing and dating the written informed consent document. Informed consent must be obtained before conducting any study-specific procedures (i.e. all of the procedures described in the protocol). The process of obtaining informed consent should be documented in the patient eSource/source documents.

Novartis will provide to investigators in a separate document a proposed informed consent form that complies with the ICH GCP guideline and regulatory requirements and is considered appropriate for this study. Any changes to the proposed consent form suggested by the investigator must be agreed to by Novartis before submission to the IRB/IEC, and a copy of the approved version must be provided to the Novartis monitor after IRB/IEC approval.

Women of child bearing potential must be informed that taking the study treatment may involve unknown risks to the fetus if pregnancy were to occur during the study and agree that in order to participate in the study they must adhere to the contraception requirement for the duration of the study. If there is any question that the patient will not reliably comply, they must not be entered in the study.

10.3 Responsibilities of the investigator and IRB/IEC

Before initiating a trial, the investigator/institution must obtain approval/favorable opinion from the Institutional Review Board/Independent Ethics Committee (IRB/IEC) for the trial protocol, written informed consent form, consent form updates, subject recruitment

procedures (e.g., advertisements) and any other written information to be provided to patients. Prior to study start, the investigator is required to sign a protocol signature page confirming his/her agreement to conduct the study in accordance with these documents and all of the instructions and procedures found in this protocol and to give access to all relevant data and records to Novartis monitors, auditors, Novartis Quality Assurance representatives, designated agents of Novartis, IRBs/IECs, and regulatory authorities as required. If an inspection of the clinical site is requested by a regulatory authority, the investigator must inform Novartis immediately that this request has been made.

10.4 Publication of study protocol and results

The key design elements of this protocol will be posted in a publicly accessible database such as clinicaltrials.gov. In addition, upon study completion and finalization of the study report the results of this trial will be either submitted for publication and/or posted in a publicly accessible database of clinical trial results.

